10.5 Hypoglycemia

Hypoglycemia will be regarded as an AE and will be recorded and documented on an AE Form. For the purposes of AE reporting, the following definitions of hypoglycemia will be used:

- Symptomatic hypoglycemia: an event during which typical symptoms of hypoglycemia are accompanied by a BG concentration ≤ 70 mg/dL
- Asymptomatic hypoglycemia: an event not accompanied by typical symptoms of hypoglycemia but with a BG concentration ≤ 50 mg/dL
- Severe hypoglycemia: an event requiring assistance of another person to actively administer carbohydrates, glucagon, or take other corrective actions

10.6 Safety Monitoring

10.6.1 Data and Safety Monitoring Board

An external DSMB will oversee the conduct of the trial, as set forth in the DSMB Charter. Additionally, the DSMB will be informed in the event of any serious and unexpected AEs. The DSMB will be informed if there are any changes to the trial protocol that could significantly impact the safety or scientific validity of the trial. A final DSMB meeting will convene after the completion of the trial.

The participation of individual patients will be discontinued if they experience:

- Seizure or unconsciousness associated with hypoglycemia and associated with participation in the trial
- Persistent nausea and vomiting thought to be related to glucagon dosing associated with participation in the trial
- Hospitalization associated with participation in the trial
- Pregnancy
- Diabetic ketoacidosis

If more than 1 patient must be withdrawn from the trial for these reasons, the trial will stop and a vote of the DSMB will be required to restart it. All AEs that are serious and unexpected but related will be reported to the DSMB within 5 working days.

Clinical Trial Protocol
ZP4207-16051

Version number: 6.0
Amendment 5.0
Date: 09 September 2016

Note that patients may discontinue participation at any time. Patients may be removed from the trial for other reasons, for instance, failure to comply with trial procedures or intercurrent illness that is unrelated to the BP but that precludes safe participation. Discontinuation of participation for these reasons will not contribute to a decision to discontinue the trial.

10.6.2 Zealand Pharma Safety Committee

The internal Zealand Pharma Safety Committee is constituted to perform ongoing safety surveillance of clinical trials within ZP4207, including this trial.

If safety signals are observed either based on reported SAEs, periodic review of laboratory parameters, planned review of all AEs reported between the safety committee meetings, or on notification of significant findings, the Safety Committee will take appropriate measures to safeguard the patients.

11 STATISTICS

For all analysis, the 2 treatment arms from Part 1 (iPhone-based BP) will be compared, and the 2 treatment arms from Part 2 (iLet) will be compared. The analysis of Part 1 will be completely separate from the analysis of Part 2.

11.1 Analysis Populations

The following analysis sets are defined in accordance with the ICH-E9 guidance:

The Full Analysis Set is based on the intention-to-treat principle and includes all randomized patients. In exceptional cases, patients from the Full Analysis Set may be excluded (will be decided in the database review [DBR] meeting). In such cases, the exclusion will be justified and documented. Patients will contribute to the evaluation “as randomized.”

The Per-Protocol Set includes all patients of the Full Analysis Set who completed the trial without any major protocol violations. Patients in the Per-Protocol Set will contribute to the evaluation “as treated.” This analysis will only be used if it is different than the Full Analysis Set.

The Safety Analysis Set includes all patients receiving at least 1 dose of the IMP. Patients in the Safety Analysis Set will contribute to the evaluation “as treated.”

Analyses of efficacy endpoints will be based on the Full Analysis Set (and the Per-Protocol Set if necessary). This decision will be made in the DBR meeting. The analysis of the safety endpoints will be based on the Safety Analysis Set.

Before data are released for statistical analysis, a blinded review of all data will take place to identify protocol deviations that may potentially affect the results. At this time, it will be determined if patients and/or data should be excluded from the analysis. Furthermore, outliers will be identified by data review according to ICH-E9.

Obviously erroneous data points may be excluded from the analyses or re-analyzed (e.g., serum concentrations). The decision to re-analyze or exclude data points from the statistical analysis is the joint responsibility of the Sponsor, the Principal Investigator, and the Trial Statistician.

Clinical Trial Protocol
ZP4207-16051

Version number: 6.0
Amendment 5.0
Date: 09 September 2016

The patients or observations to be excluded and the reason for their exclusion will be documented and signed by those responsible prior to database release. The documentation will be stored together with the remaining trial documentation. The patients and observations excluded from analysis sets, and the reason for this, will be described in the clinical trial report.

11.2 Statistical Methods

Medpace will be responsible for the statistical analysis. The statistical planning and conduct of analyses of the data from this trial will follow the principles defined in relevant ICH guidelines and Medpace's biostatistical standard operating procedures (SOPs). A general description of the statistical methods to be used is given in this section, specific details will be provided in the Statistical Analysis Plan (SAP), which will be prepared before database lock. All statistical analyses will be performed using SAS® (SAS Institute Inc., Cary, North Carolina, USA), version 9.3 or later.

11.2.1 Analysis of Safety

The following variables will be evaluated according to treatment for safety purposes:

Adverse Events

All AEs will be coded using the latest version of Medical Dictionary for Regulatory Activities (MedDRA). Individual AEs will be presented in a listing including relationship to trial product/device, severity, and treatment period at onset. If more than 20 treatment-emergent AEs (AEs with onset after [first] dosing at Visit 3 until the Follow-up Visit 6) are registered, a summary table including number of AEs, number of patients with at least 1 AE, and percentage of exposed patients with at least 1 AE will be made by system organ class and treatment period at onset.

Local Tolerability

Local tolerability at the injection site will be summarized using descriptive statistics as appropriate.

Laboratory Safety Assessments

Laboratory assessments will be summarized. A listing of abnormal values will be provided.

Physical Examination

A frequency table will show the number and percentage of physical examination results.

Vital Signs

Vital signs will be summarized using descriptive statistics.

12-lead ECG

The Investigator's evaluations of 12-lead ECGs will be summarized and abnormal individual evaluations will be listed together with the Investigator's comments. Changes in 12-lead ECG between measurements will be recorded as AEs if the Investigator judges them to be clinically significant.

Clinical Trial Protocol
ZP4207-16051

Version number: 6.0
Amendment 5.0
Date: 09 September 2016

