[Part 2 of 3 of the document. The other parts are not shown.]

- CGM glucose every 5 minutes from the Dexcom G4 Platinum CGM
- All BG measurements taken
- Insulin total dose by the BP and the patient's own insulin pump
- Glucagon total dose
- Timing and content of the meal eaten and carbohydrate amount
- Timing of meal announcement and size of meal announced
- Timing and glucose values at calibrations
- Timing and amount of carbohydrates taken for hypoglycemia
- Data from a questionnaire about attitudes and expectations regarding the BP before and after each treatment arm (see [Appendix C](#))
- Time patients were not under BP control for any reason
- List of technical faults associated with the BP including cause and resolution
- ZP4207/glucagon sampling will be collected at least hourly. If BG is <150 mg/dL, more frequent samples for plasma ZP4207/glucagon may be drawn at the discretion of the Investigator.
- Plasma glucose sampling will be collected at least hourly in parallel with ZP4207/glucagon exposure sampling. If BG is <150 mg/dL, then sampling will be every 30 minutes. If BG is <100 mg/dL, then sampling will be every 20 minutes. If BG is <80 mg/dL, then sampling will be every 10 minutes.
- Nausea and infusion site pain on a VAS at visit start (after insertion and before any drug administration), hourly, and at visit end
- Infusion site reaction according to the Draize scale at visit start (after insertion and before any drug administration), hourly, and at visit end
- Patient reports of symptoms, any other complaints, and AEs
- Vital signs including body temperature and blood pressure (at visit start and visit end) and weight
- Concomitant medications

Clinical Trial Protocol
ZP4207-16051

Version number: 6.0
Amendment 5.0
Date: 09 September 2016

- Chemistry and hematology samples (see [Appendix B](#)) at visit start and visit end
- ADA (Visit 3 only)
- 12-lead ECG at visit start and visit end
- Urine HCG pregnancy test for women of childbearing potential

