10.1.1 Follow-up of Adverse Events

All AEs that are ongoing at the end of the patient's participation in the trial will be followed-up until the event is resolved or reaches a satisfactory outcome as deemed by the Investigator. Follow-up actions for all serious adverse events (SAEs) will be performed according to appropriate clinical care practices and may depend on the nature of the event. These will be determined after internal review and/or Sponsor review. The follow-up information should only include new (updated and/or additional) information that reflects the situation at the time of the Investigator's signature.

Follow-up information on (S)AEs will be updated using the (S)AE Form. If a non-serious event becomes serious during the follow-up, the AE Form and SAE Form must be used and reporting timelines follow those of an SAE.

The Investigator must forward follow-up information on SAEs, and if previously non-serious AEs become SAEs, to the Sponsor.

Clinical Trial Protocol
ZP4207-16051

Version number: 6.0
Amendment 5.0
Date: 09 September 2016

10.1.2 **Precautions**

Normal precautions taken for a human trial will be taken during this trial. Qualified and well-trained physicians and medical staff will instruct the patients. During a patient's participation in the trial, the Investigator should ensure that adequate medical care is provided to the patient for any AEs, including clinically significant laboratory values related to the trial. The Investigator should inform the patient when medical care is needed for intercurrent illnesses of which the Investigator becomes aware.

For further information on safety precautions for ZP4207, Lilly glucagon, and Lilly Humalog, please refer to the current version of the Investigator's Brochure (IB) for ZP4207 ([Zealand Pharma A/S, 2015](#), or any updates hereof), and the SPC for Glucagon ([Eli Lilly, 2012](#)) and Humalog ([Eli Lilly, 2015](#)), respectively.

10.1.3 **Assessment of Adverse Events by the Investigator**

Intensity of an Adverse Event

The maximum intensity (severity) of all AEs must be assessed by the Investigator and documented. Severity should be graded when the AE outcome is known:

- **Mild:** A type of AE that is usually transient and may require only minimal treatment or therapeutic intervention. The event does not generally interfere with usual activities of daily living.

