10.3 Adverse Event Reporting – Procedures for Investigators

The Principal Investigator and co-investigators will review any AEs and report any SAEs to the Sponsor as soon as possible and within 24 hours of obtaining knowledge of the event. The Principal Investigator and co-investigators will promptly report AEs to the Partner’s Institutional Review Board (IRB) and to the BU IRB (unless oversight is ceded by the BU IRB to the Partners IRB), in accordance with local requirements.

[name] is the Sponsor of the Investigational Device Exception for the BP and Zealand Pharma A/S is the Sponsor of the IND for ZP4207.

Clinical Trial Protocol
ZP4207-16051

Version number: 6.0
Amendment 5.0
Date: 09 September 2016

Reports of AEs will be submitted to the FDA in compliance with the terms of the Code of Federal Regulations.

All events meeting the definition of an AE must be collected and reported from the first trial-related activity from Visit 3 until the end of the post-treatment follow-up period. At each contact with the site (visit or telephone, excluding safety visits, where the patient is not seeing the Investigator or staff [e.g., visits to the laboratory], the patient must be asked about AEs. All AEs, either observed by the Investigator or reported by the patient, must be recorded by the Investigator and evaluated.

The Investigator should record the diagnosis, if possible. If no diagnosis can be made, the Investigator should record each sign and symptom as individual AEs. All AEs must be recorded by the Investigator. One single AE Form must be used per AE from start to resolution. For SAEs, the SAE Form must also be completed.

AE information should include the following:

- Patient identification number on all pages
- Date and time of treatment start
- Date and time of onset and date of outcome
- Date and time of Investigator's first information on the (S)AE
- Seriousness
- Severity
- Causal relationship with IMP ZP4207
- Causal relationship with IMP insulin
- Causal relationship with IMP glucagon
- Causal relationship with medical device
- Causal relationship with procedures
- Interruption or withdrawal of treatment with IMP or medical device and other measures taken
- Outcome

All AEs are coded; details are described in the trial specific Data Management Plan.

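### Treatment-emergent AEs are defined by onset alone, so worsening on drug goes uncounted when the AE was open before the first Visit 3 dose, or was carried into Visit 4

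*Protocol*

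**What the plan says.** All references are to protocol version 6.0; the SAP is not at hand.

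- **Definition (11.2.1).** Treatment-emergent AEs are "AEs with onset after [first] dosing at Visit 3 until the Follow-up Visit 6". An increase in severity is not mentioned.
- **Table (11.2.1).** The summary table is conditional: "If more than 20 treatment-emergent AEs" are registered, it is produced, and it "will be made by system organ class and treatment period at onset". It gives the number of AEs and the number and percentage of patients with at least one. The section opens by saying that safety variables are evaluated according to treatment.
- **Listing (11.2.1).** "Individual AEs will be presented in a listing including relationship to trial product/device, severity, and treatment period at onset". The listing is not limited to treatment-emergent events.
- **Recording (10.3 and 10.1.3).** "One single AE Form must be used per AE from start to resolution". "The maximum intensity (severity) of all AEs must be assessed by the Investigator and documented", with grading done once the outcome is known. The items required on the form include onset date and time, outcome date and severity. A date of worsening is not among them.
- **Collection window (10.1 and 10.3).** AEs are collected from the first trial-related activity of Visit 3, which precedes dosing. Section 10.1 also makes a clinically significant worsening of a concomitant illness an AE in its own right.
- **Pre-dose assessments (7.4.2).** Nausea, infusion site pain and site reaction are recorded "at visit start (after insertion and before any drug administration"), then hourly and at visit end.

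**The concern.** Number and type of AEs is the first component listed under the primary endpoint in section 8.1. A table meant to compare two products within patients should show a deterioration under the product being given when it happened. A rule based on onset alone does this for a new event, but not for an event that is already open when a product is started.

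This design produces such events in two places. At Visit 3 there is an interval in which AEs are already being collected, infusion sets are already in place and no drug has been given. At Visit 4 the patient starts the other product 24 hours to 3 weeks after the first (section 7.4 and Appendix A), so an event from the first period may still be open.

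The recording rules make the problem harder to repair later. A SAP can redefine treatment-emergent, but if the eCRF captures only the onset date, the outcome date and one maximum severity, the date on which the event became worse may not be in the database.

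**Working it through.** The protocol states no figure to reproduce. The check sets the definition, the table rule and the recording rules side by side and follows each type of event through them.

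1. **Starts after dosing and worsens in the same period.** Onset and worsening belong to the same product. The event is counted and correctly placed.

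2. **Illness present at screening that worsens after dosing.** Under 10.1 a clinically significant worsening is itself an AE, with its own post-dose onset. It is counted in the right period.

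3. **Starts at Visit 3 after the first trial-related activity but before the first dose, then worsens on drug.** The single form keeps the pre-dose onset. The event fails the definition, does not count toward the threshold of more than 20, and is absent from the table. It appears only in the listing. The rule is also uneven between visits: a pre-dose event at Visit 4 has its onset after first dosing at Visit 3, so it meets the definition and is counted.

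4. **Starts in the first period, is open at Visit 4 and worsens on the second product.** It remains one record. Because the table is "made by system organ class and treatment period at onset", the event is shown under the first product and nothing is added under the second. In the listing, the overall maximum severity stands beside the first period, even if that severity was reached on the second product.

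Only types 3 and 4 are mishandled.

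**Size for one patient**

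- Section 11.2.4 expects 20 to 24 randomized patients, and section 11 analyses the two parts separately. Assuming an equal split, that is 20/2 = 10 to 24/2 = 12 patients per part, each exposed to both products.
- One patient is then 1/10 = 10 percentage points of incidence, or 1/12 = 8.3 points.
- In type 3, the product given at Visit 3 loses one patient and the other product is unchanged. The between-product difference moves by 8.3 to 10 points.
- In type 4, the onset properly stays with the first product and the second product is short by one patient. The difference again moves by 8.3 to 10 points.
- These are upper limits. The percentage counts patients with at least one AE, so if the patient already has another AE in the same system organ class and period, the percentage does not move at all.

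**Direction**

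The order of treatments is randomized in blocks of 2 (Appendix A, footnote 1). About half the patients receive each product at Visit 3, so by design the type 3 loss falls equally on both products.

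The protocol gives no rate for either type, so the expected number of affected events cannot be computed.

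**The case against.** The case for leaving the text alone has real weight.

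- **Other data cover the likeliest examples.** Site reactions, pain and nausea are measured before drug and then hourly at each treatment visit. The Draize scale and both VAS scores are separate components of the primary endpoint, and local tolerability has its own summary in 11.2.1. For these, worsening after dosing is visible by visit, and so by product. This stands; the gap matters mainly for other AEs, such as headache.
- **Nothing disappears from the report.** Every AE is listed, and 10.3 records causality separately for ZP4207, insulin, glucagon, device and procedures. With about 10 patients per part, a reader can go through the listing case by case. This stands, but the listing too carries only the period at onset and a severity.
- **Recording more is not forbidden.** Section 10.1.3 requires the maximum severity and does not exclude other entries. Section 10.1.1 provides for updated follow-up information, and eCRF details are left to the Data Management Plan. So it cannot be said that the timing of worsening will be lost, only that the protocol does not require it to be captured.
- **This is SAP detail.** Section 11.2 leaves specifics to the SAP. That would answer a silence, but here the protocol states the definition and the tabulation rule itself, and what is captured has to be settled before data collection.

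A reader might infer several stronger things that the documents do not support. It is not true that any event worsening after dosing is lost or misassigned: worsening within a period and worsening of a concomitant illness are handled. A 20-point shift in the between-product difference would need a patient to move entirely from one product to the other, whereas the onset rightly stays with the first. The pre-dose loss does not work for or against ZP4207 in particular, because the order is randomized. Nor are local reactions hidden, given the hourly measurements.

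**Conclusion.** The point holds in a narrow form. As written, section 11.2.1 leaves out AEs that open at Visit 3 before the first dose and worsen on drug, and shows AEs carried into Visit 4 that worsen on the second product only under the first. This is a fixed rule in a component of the primary endpoint, and it should be corrected.

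The likely effect is small. One affected patient changes an incidence and the between-product difference by at most about 10 percentage points. That rests on 10 to 12 patients per part and on the patient having no other AE in that cell. The number of such patients is unknown. The type 3 loss is balanced between products by the randomized order, and listings, causality per product and the hourly scales reduce the harm further. The SAP may contain a worsening rule, but it would work only if dated severity changes are collected.

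**What to change.** Make two changes.

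- **Section 11.2.1.** Extend the definition to onset, or increase in severity, after dosing. Count the increase under the product being given at that time, and keep the event's onset under its own period.
- **Section 10.3.** Require that an open AE which increases in severity after dosing starts at either treatment visit be recorded as a new AE, or on the same form with the date, time, and severity before and after. If the new-AE option is chosen, qualify the single-form sentence to match.

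The cost is one sentence in each section and one added eCRF field. AE counts may be slightly higher, and the threshold for the summary table may be reached slightly sooner.

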11.2.2 Analysis of Efficacy

The analysis of BP function endpoints and glycemic endpoints will be on an intention-to-treat basis. In cases where a treatment arm was not completed (and that arm was not repeated according to protocol criteria), available data from that arm will be used in the data analysis.

The Shapiro-Wilk test will be used to determine the normality of the residuals for each comparison. Summary tables that display descriptive statistics, including percentages, means or medians, and standard deviation and/or ranges, as appropriate, will be provided.

A paired t-test or the Wilcoxon signed rank test for comparison of means with normally or non-normally distributed residuals, respectively, will be used. In a secondary analysis, any period effect and any interaction between treatment and period will be looked for, although no such interaction is predicted for the efficacy outcome. Further details will be included in the SAP.

The number of patients and proportions of severe hypoglycemic events, symptomatic hypoglycemia, and carbohydrate interventions due to hypoglycemia with the event counts will be summarized descriptively, and the proportions will be analyzed by a Fisher's exact test if data allow.

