7.4.4 Response to Hyperglycemia

- Trial staff will check the infusion site, BP, and insulin pump for normal operation any time BG is >300 mg/dL. If there is any suspicion of infusion set malfunction, the site should be replaced. Trial staff will check the BP for any malfunction and correct any problems that are found. If the BG remains >300 mg/dL for 2 hours despite troubleshooting, blood ketones will be measured. If the blood ketone result is >1.5 mmol/L, the visit will be stopped and rescheduled. The patient will be provided with insulin and a syringe to give an injection based on their correction factor.
- If a patient experiences diabetic ketoacidosis, his or her participation in the trial will be discontinued.
- If no correctable fault is found, but there is doubt regarding the correct function of the BP system, the treatment visit may be stopped and the visit rescheduled.

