8.2 Secondary Endpoints

The secondary endpoints include measurements of BP function as well as glycemic and non-glycemic measurements.

Clinical Trial Protocol
ZP4207-16051

Version number: 6.0
Amendment 5.0
Date: 09 September 2016

8.2.1 **Bionic Pancreas Function**

This endpoint data will be generated from the BP data during each treatment visit:

- Average percent insulin dose amounts calculated by the BP control algorithm that are successfully delivered by the pump
- Average percent glucagon/ZP4207 dose amounts calculated by the BP control algorithm that are successfully delivered by the pump
- Average percent dose amounts successfully issued to the pump by the BP control algorithm that are successfully delivered by the pump (calculated doses are not issued unless the pump is accessible and its delivery channel is available)
 - Average percent insulin dose amounts successfully issued to the pump by the BP control algorithm that are successfully delivered by the pump
 - Average percent glucagon/ZP4207 dose amounts successfully issued to the pump by the BP control algorithm that are successfully delivered by the pump
- Average percent dose amounts calculated by the BP algorithm that are successfully issued to the pump by the BP (calculated doses are not issued unless the pump is accessible and its delivery channel is available)
 - Average percent insulin dose amounts calculated by the BP control algorithm that are successfully issued by the BP
 - Average percent glucagon/ZP4207 dose amounts calculated by the BP control algorithm that are successfully issued by the BP
- Average percent of 5-minute steps during which the BP is functioning nominally in all respects based on real-time CGM data (new CGM glucose reading captured, dose calculated, and dose issued to pumps)
- Average percent of 5-minute steps during which the BP is functioning nominally with or without a new CGM glucose reading captured (dose calculated and dose issued to pumps). If a CGM signal is not available, the dose calculated may be based on weight or historical basal rates.
- CGM reliability index, calculated as percent of possible values actually recorded by CGM
- CGM Mean Absolute Relative Difference versus time-stamped BG values from meter download
- List of technical faults associated with the BP including cause and resolution

8.2.2 **Glycemic**

All of following metrics will be generated from the Dexcom G4 Platinum CGM data during each treatment visit:

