- Patients will exercise on a stationary bike with a heart rate from 120-140 beats per minute for a total of 4,000 heart beats (approximately 30 minutes). Patients will rate their exercise intensity using the Borg scale every 5 minutes, with the target intensity level between 12 and 14. Heart rate will be measured every 5 minutes.
- BG measurements will be obtained off of the IV line every 10 minutes. If BG is <80 mg/dL, BG measurements will be obtained off of the IV line every 5 minutes.
 - Carbohydrates will be given for any BG <50 mg/dL according to the following protocol: Dextrose (g) = BSA (m²)/[1.7 m² (women) or 1.9 m² (men)] *15 g.
 - Repeat treatments will be given at 15-minute intervals as long as BG remains <50 mg/dL.
- If there is an interruption in the Dexcom CGM output, trial staff will assist the patient in recovering CGM data streaming. If this requires replacement of the CGM sensor, BGs will be checked every 10 minutes (every 5 minutes if BG is <80 mg/dL) using blood from the IV until the CGM is able to be calibrated again. These BGs will be entered into the BP, which will treat them as CGM values and dose insulin and/or glucagon appropriately.
- If there is a complete failure of the BP operation, patients will take over their own BG control using their personal insulin pump until the BP can be brought back online. If BP control cannot be promptly resumed (e.g., within 30 minutes), the patient may be asked to repeat that trial day once.
- Patients may choose to withdraw from the trial at any time. If they withdraw from the trial, they should alert a provider immediately.
- Just prior to the end of the study visit, vital signs including body temperature and blood pressure will be obtained and a 12-lead ECG will be performed.
- After approximately Hour 8, but not earlier than at least 60 minutes after end of exercise, the BP will be stopped and the patient will continue with their personal insulin pump.

Clinical Trial Protocol
ZP4207-16051

Version number: 5.0
Amendment 4.0
Date: 02 September 2016

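### The efficacy analysis is labelled intention-to-treat, yet its wording implies that a repeated visit replaces one stopped for device failure or hyperglycemia, so reliability and hyperglycemia means are selected on outcome

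*Protocol*

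**What the plan says.** Protocol version 6.0, section 11.2.2, opens with: "The analysis of BP function endpoints and glycemic endpoints will be on an intention-to-treat basis". The next sentence names the data that enter the analysis when an arm is incomplete: "In cases where a treatment arm was not completed (and that arm was not repeated according to protocol criteria), available data from that arm".

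Three provisions lead to a second attempt at a started visit:

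- Section 7.4.4 (version 6.0) calls for a ketone test when BG stays above 300 mg/dL for 2 hours despite troubleshooting. It continues: "If the blood ketone result is >1.5 mmol/L, the visit will be stopped and rescheduled".
- The same section covers doubt about BP function with no correctable fault found: "the treatment visit may be stopped and the visit rescheduled".
- Section 7.4.1 covers complete failure of BP operation: "If BP control cannot be promptly resumed (e.g., within 30 minutes), the patient may be asked to repeat that trial day once". This text is from version 5.0, because section 7.4.1 of version 6.0 is not in the text available for this review.

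The secondary endpoints in section 8.2 include "Average percent of 5-minute steps during which the BP is functioning nominally in all respects based on real-time CGM data", the percentages of calculated doses issued and delivered, time above 250 and 300 mg/dL, and mean CGM glucose.

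**The concern.** The events that make a visit eligible for a second attempt are what the secondary endpoints measure. If the repeat stands in for the first attempt, a day leaves the arm mean because it scored badly on the variable being averaged. That is the opposite of what the intention-to-treat label promises.

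Two of the three triggers are discretionary, and the decision is taken with the drug known. The blinded data review in section 11.1 comes later and cannot undo it. On glucose the selection is also one-sided: section 7.4.3, on hypoglycemia, offers a backup system and no rescheduled visit.

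Device reliability is a stated secondary objective (section 2.2, version 5.0). The two parts are analysed separately with about 10 patients each, so a single visit can move a mean visibly.

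A smaller issue arises when a stopped visit is not repeated. A partial visit is then paired with a full one. Lunch falls at about Hour 3 to 4 and exercise at about Hour 6 to 7 (Appendix A, footnotes 18 and 19), so the two visits may cover different challenges. Totals such as grams of carbohydrate also accrue over fewer hours.

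**Working it through.** The protocol gives no power calculation or expected failure rate, so there is no figure of its own to reproduce. The sizes below are illustrations.

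**Inputs.** A visit lasts about 8 hours (section 7.4.1, version 5.0), which is 8 × 12 = 96 five-minute steps. Section 11.2.4 expects 20 to 24 randomized patients over two parts, or 10 to 12 per part if split evenly; 10 is used here. Assumptions: one visit in the arm fails and is replaced by a clean repeat, and all other steps are nominal.

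**1. Nominal function.** Shift in the arm mean = (share of steps lost in the failed visit) ÷ 10. The share depends on the denominator, which section 8.2.1 does not define for a stopped visit.

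| Failure at | Observed steps only, visit ended 30 min later | All 96 scheduled steps |
|---|---|---|
| Hour 2 | 6/30 = 20.0%, shift 2.0 points | 72/96 = 75%, shift 7.5 points |
| Hour 4 | 6/54 = 11.1%, shift 1.1 points | 48/96 = 50%, shift 5.0 points |
| Hour 6 | 6/78 = 7.7%, shift 0.8 points | 24/96 = 25%, shift 2.5 points |

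With 12 patients the Hour 4 shifts are 11.1/12 = 0.9 and 50/12 = 4.2 points.

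**2. Time above 300 mg/dL.** The ketone test requires at least 2 hours, or 24 steps. Over 8 hours that is 24/96 = 25%, or 2.5 points on a mean of 10. As a partial visit stopped at Hour 4 it is 24/48 = 50%, or 5.0 points. Replaced by a repeat with no such time, it contributes 0.

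**3. Chance that a part is affected.** A part of 10 patients has 20 treatment visits. P(at least one trigger) = 1 − (1 − p)^20. For assumed per-visit rates p of 2%, 5%, 10% and 20% this is 33%, 64%, 88% and 99%.

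**4. Drug difference.** Assume 98% nominal on a good day, 49% on a day failing midway, and at most one repeat.

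- First attempts: mean = (1 − p) × 98 + p × 49.
- Repeat replacing the first attempt: mean = (1 − p) × 98 + p × [(1 − p) × 98 + p × 49].
- Equal failure, p = 10% with both drugs: both means move from 93.1 to 97.5, and the difference stays at 0.
- Unequal failure, 20% against 10%: first attempts give 88.2 − 93.1 = −4.9 points; after replacement, 96.0 − 97.5 = −1.5 points.

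**5. Unrepeated partial visit.** Assume the same profile for both drugs: 1% of time below 60 mg/dL before Hour 6, and 6% in Hours 6 to 8. A full visit gives (6 × 1 + 2 × 6)/8 = 2.25%, and a visit stopped before exercise gives 1.0%. The paired difference is −1.25 points with no drug effect.

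**The case against.** The strongest reply is that replacement is never written out. Section 11.2.2 says what happens when an arm was not repeated and is silent on which attempt counts when it was. Sections 11.2 and 11.2.2 leave details to the SAP, where attempt selection and window matching would ordinarily sit. This stands in part: the lack of a common window is not by itself a protocol error. But the parenthesis has little purpose unless a repeat displaces the first attempt, no text shown keeps the first attempt, and the rule sits directly under an intention-to-treat label. A SAP that follows it inherits the selection.

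Other limits also stand:

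- The device-failure repeat is seen only in version 5.0. Section 11.2.2 and the two hyperglycemia provisions, all version 6.0, carry the point without it.
- A mandatory stop needs ketones above 1.5 mmol/L as well as 2 hours above 300 mg/dL. Under section 7.4.1 of version 5.0 patients also receive twice their usual basal rate from their own pump until exercise, so such stops may be rare. The documents give no rate.
- Insulin and glucagon per kg are listed as non-glycemic (section 8.2.3), while the sentence introducing the rule names only BP-function and glycemic endpoints.

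A reader might infer that failures vanish from the trial record. They do not: the fault list is not restricted to retained visits, time off BP control is collected (section 7.4.2), and device deficiencies are documented and reported (section 10.3). A reader might also infer that the ZP4207 versus glucagon comparison is necessarily biased. Step 4 shows no such bias when triggers are equally frequent, and both arms of a part use the same device and algorithm.

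**Conclusion.** The point holds for the arm means of device reliability and hyperglycemia. Read naturally, section 11.2.2 lets a repeat replace a visit that was stopped for what the endpoint measures, and this cannot be called intention-to-treat. With 10 patients per arm, one replaced Hour 4 failure flatters mean nominal function by about 1.1 to 5.0 points depending on the denominator, and the figure varies with the hour of failure. The drug difference is affected only if triggers differ by drug, in which case the illustration pulls it toward zero.

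The number of affected visits is unknown, and replacement is implied, not stated. The primary endpoint is safety and tolerability, analysed on the Safety Analysis Set, and is untouched. This should be fixed, but it does not threaten the trial's main conclusion.

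**What to change.** Amend section 11.2.2, and the SAP to match:

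1. Compute BP-function endpoints over all started visits, including those later repeated, and count scheduled steps lost to a device-caused stop as not nominal.
2. For glycemic endpoints, state which attempt is analysed. Report results both with the first attempt and with the repeat, and do not call a repeat-only analysis intention-to-treat. Reporting both avoids discarding a complete repeat.
3. For truncated visits that are not repeated, add a sensitivity analysis over the hours common to both of the patient's visits, with totals per hour.
4. Report stopped, rescheduled and repeated visits, with reasons, by treatment.

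The cost is wording and some extra analysis, since the device data are already stored (section 12.1). The reliability figure may become slightly less favourable. The clinical stopping and rescheduling rules stay as they are.
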